Dose levels to be considered for the next cohort will be based on evaluating three potential recommendations by BLRM (-Copula): escalate, de-escalate, or stay at same dose level. Final dose selection for next cohort/dose level will be made in conjunction with the data available on all dosed subjects, including clinical and laboratory safety assessments, PK, [REDACTED] data, will not allow escalation by more than one dose level and will be made after discussion and agreement between Investigators and Medical Monitor. Accordingly, intermediate or lower doses, or less frequent dosing of BMS-986156 may be tested if none of the planned doses/schedules is found to be tolerated as monotherapy or in combination with nivolumab. Up to an additional 9 subjects may be enrolled in an already DLT cleared cohort to collect additional PK, [REDACTED] and safety data to better understand any dose response relationship.

Approximately 30 subjects each will be treated in each dose escalation phases in monotherapy (Part A) and combination therapy (Part B).

During dose escalation phase, once a dose level has been decided, a set of approximately 3 subjects will be treated at that specified dose level. Cohort tolerability assessment and subsequent dose recommendation will occur according to BLRM (-Copula) recommendation and after at least 2 subjects complete the 4 week DLT observation period. If the potential DLT occurring in the 3rd evaluable subject regarding the specific dose level does not influence the dose recommendation by BLRM (-Copula), the BLRM (-Copula) recommended next dose level may proceed without waiting for the 3rd subject to complete the corresponding DLT observation period, after discussion and agreement between Sponsor and Investigators.

Subjects must be observed for a total of 28 days following the first therapy dose to be considered evaluable for DLT. Subjects discontinued during DLT observation period due to DLT are also considered as evaluable for DLT. Continuous re-assessment of dose recommendation by BLRM (-Copula) will also be carried out at each dose levels.

The MTD/MAD/alternate dose(s) of BMS-986156 selected for cohort expansion in Parts C and D will be based on evaluating the recommendation from BLRM and a synthesis of all available data, including clinical and laboratory safety assessments, PK, [REDACTED] and efficacy data, from all treated patients at each dose level up to the MTD/MAD.

No intra-subject dose escalation or reduction is allowed.

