4.3.1 Dose-limiting Toxicities

AEs will be graded according to the NCI CTCAE v4.03.

Non-hematologic Dose-limiting Toxicity (DLT)

A. Hepatic Non-hematologic DLT

Any one of the following study drug-related events will be considered a hepatic DLT:

- Any Grade ≥ 3 elevation of AST, ALT, or total bilirubin
- Grade 2 AST or ALT with symptomatic liver inflammation (e.g., right upper quadrant tenderness, jaundice, pruritus)
- AST or ALT $> 3 \times$ ULN and concurrent total bilirubin $> 2 \times$ ULN without initial findings of cholestasis (elevated serum ALP (e.g., findings consistent with Hy's law or FDA definition of potential drug-induced liver injury or pDILI). Note that this special category of DLT uses ULN rather than CTC Grade for definition

B. Non-hepatic Non-hematologic DLT

Any of the following events will be considered a Non-Hepatic Non-Hematologic DLT:

- Any Grade 2 drug-related uveitis or eye pain or blurred vision that does not respond to topical therapy and does not improve to Grade 1 severity ≤ 2 weeks OR requires systemic treatment
- Grade 3 drug-related uveitis, pneumonitis, bronchospasm, neurologic toxicity, hypersensitivity reaction, or infusion reaction of any duration requires discontinuation
- Any Grade 3 or greater non-dermatologic, non-hepatic non-hematologic study drug-related toxicity will be considered a dose-limiting toxicity with the following specific EXCEPTIONS:
 - Grade 3 or grade 4 electrolyte abnormalities that are not complicated by associated clinical adverse experiences, last ≤ 48 hours and either resolve spontaneously or respond to conventional medical intervention
 - Grade 3 nausea, vomiting or diarrhea that lasts less than 48 hours, and either resolves spontaneously or responds to conventional medical intervention
 - Isolated Grade 3 elevation of amylase or lipase not associated with clinical or radiographic evidence of pancreatitis
 - Isolated Grade 3 fever not associated with hemodynamic compromise (eg, hypotension, clinical or laboratory evidence of impaired end-organ perfusion)
 - Grade 3 endocrinopathy that is well controlled by hormone replacement
 - Grade 3 tumor flare (defined as pain, irritation, or rash that localizes to sites of known or suspected tumor)
 - Grade 3 fatigue for ≤ 7 days
 - Grade 3 infusion reaction that returns to Grade 1 in ≤ 6 hours

C. Dermatologic DLT

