- Grade 3/4 rash if no improvement (i.e. resolution to \leq Grade 1) after a 1-2 week infusion delay. Subjects who have not experienced a Grade 3 drug-related skin AE may resume treatment in the presence of Grade 2 skin toxicity.

D. Hematologic DLT (Study Drug-related)

- Grade 4 neutropenia \geq 5 days in duration
- Grade 4 thrombocytopenia or Grade 3 thrombocytopenia with clinically significant bleeding, or any requirement for platelet transfusion
- Grade 4 anemia not explained by underlying disease
- Grade 4 febrile neutropenia
- Grade 3 febrile neutropenia that lasts > 48 hours
- Grade \geq 3 hemolysis (ie, requiring transfusion or medical intervention such as steroids)

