4.3.6 Guidelines for Permanent Discontinuation

Subjects will be required to permanently discontinue both study drugs for the following AEs:

- Any drug related AE occurring at any time that meets DLT criteria as outlined in [Section 4.3.1](#) will require permanent discontinuation with the following **exceptions**:
 - a) Grade 3 diarrhea, nausea, vomiting, or abdominal pain that returns to grade 1 or baseline within 3 days with medical intervention;
 - b) Grade 3 pruritus or rash that returns to grade 1 or baseline within 7 days or baseline with medical intervention;
 - c) Grade 4 electrolyte abnormalities that \leq 72 hours in duration;
 - d) Grade 4 neutropenia \leq 5 days in duration;
 - e) Grade 4 increase in amylase or lipase that is not associated with clinical or radiographic evidence of pancreatitis;
 - f) Grade 4 lymphopenia \leq 5 days in duration.
- Any dosing delay lasting > 6 weeks will be cause for permanent discontinuation. Extensions to the period of dose delays may be granted for individual subjects on a case by case basis after specific consultation and agreement between the Investigator and BMS Medical Monitor in settings where benefit/risk may justify continued study therapy (e.g., subject deriving clinical benefit who requires prolonged steroid taper for management of non-DLT irAEs, or experiences delays for management of a non-drug-related AE).
- Accordingly, dosing delays to allow for prolonged steroid tapers to manage drug-related AEs are allowed. Additionally, dosing delays > 6 weeks that occur for non-drug-related reasons may be allowed if approved by the BMS Medical Monitor.
- Prior to re-initiating treatment in a subject with a dosing delay lasting > 6 weeks, the BMS Medical Monitor must be consulted.
- Tumor assessments should continue as per protocol even if dosing is delayed.

All subjects who discontinue IP should comply with protocol specified follow-up procedures as outlined in [Section 3.3](#). The only exception to this requirement is when a subject withdraws consent for all study procedures including post-treatment study follow-up or loses the ability to consent freely (e.g., is imprisoned or involuntarily incarcerated for the treatment of either a psychiatric or physical illness).

If study treatment is discontinued prior to the subject's completion of the study, the reason for the discontinuation must be documented in the subject's medical records and entered on the appropriate CRF page.

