Patients on IV steroids may be switched to an equivalent dose of oral corticosteroids (e.g. prednisone) at start of tapering or earlier, once sustained clinical improvement is observed. Lower bioavailability of oral corticosteroids should be taken into account when switching to the equivalent dose of oral corticosteroids.

Hepatic Adverse Event Management Algorithm

Rule out non-inflammatory causes. If non-inflammatory cause, treat accordingly and continue I-O therapy. Consider imaging for obstruction.

[figure not shown]
Patients on IV steroids may be switched to an equivalent dose of oral corticosteroids (e.g. prednisone) at start of tapering or earlier, once sustained clinical improvement is observed. Lower bioavailability of oral corticosteroids should be taken into account when switching to the equivalent dose of oral corticosteroids.

*I-O therapy may be delayed rather than discontinued if AST/ALT ≤ 8 x ULN or T.bili ≤ 5 x ULN.

**The recommended starting dose for grade 4 hepatitis is 2 mg/kg/day methylprednisolone IV.

Endocrinopathy Management Algorithm

[figure not shown]
Rule out non-inflammatory causes. If non-inflammatory cause, treat accordingly and continue I-O therapy. Consider visual field testing, endocrinology consultation, and imaging.

Patients on IV steroids may be switched to an equivalent dose of oral corticosteroids (e.g. prednisone) at start of tapering or earlier, once sustained clinical improvement is observed. Lower bioavailability of oral corticosteroids should be taken into account when switching to the equivalent dose of oral corticosteroids.

Skin Adverse Event Management Algorithm

Rule out non-inflammatory causes. If non-inflammatory cause, treat accordingly and continue I-O therapy.

[figure not shown]
Patients on IV steroids may be switched to an equivalent dose of oral corticosteroids (e.g. prednisone) at start of tapering or earlier, once sustained clinical improvement is observed. Lower bioavailability of oral corticosteroids should be taken into account when switching to the equivalent dose of oral corticosteroids.

*Refer to NCI CTCAE v4 for term-specific grading criteria.

^If SJS/TEN is suspected, withhold I-O therapy and refer patient for specialized care for assessment and treatment. If SJS or TEN is diagnosed, permanently discontinue I-O therapy.

Neurological Adverse Event Management Algorithm

Rule out non-inflammatory causes. If non-inflammatory cause, treat accordingly and continue I-O therapy.

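### Severe skin events other than rash, and those that end treatment before an infusion is delayed, are not DLTs unless labelled as a hypersensitivity or infusion reaction

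*Combined protocol and SAP*

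**What the plan says.** Section 4.3.1 defines DLTs in four groups: hepatic (A), non-hepatic non-hematologic (B), dermatologic (C) and hematologic (D).

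- **B, default rule:** "Any Grade 3 or greater non-dermatologic, non-hepatic non-hematologic study drug-related toxicity will be considered a dose-limiting toxicity", followed by listed exceptions.
- **B, named reactions:** "Grade 3 drug-related uveitis, pneumonitis, bronchospasm, neurologic toxicity, hypersensitivity reaction, or infusion reaction of any duration requires discontinuation".
- **C, the only skin criterion:** "Grade 3/4 rash if no improvement (i.e. resolution to" Grade 1 or less, judged after the infusion has been delayed by one to two weeks. The next sentence, "Subjects who have not experienced a Grade 3 drug-related skin AE may resume treatment" with Grade 2 skin toxicity present, is a rule about restarting therapy and does not define a DLT.
- **Appendix 4, skin algorithm footnote:** therapy is withheld when SJS/TEN is suspected, and then "If SJS or TEN is diagnosed, permanently discontinue I-O therapy".
- **Section 3.4.1, evaluability:** "Subjects must be observed for a total of 28 days following the first therapy dose to be considered evaluable for DLT". A subject who stops earlier is still evaluable, but only if the reason for stopping was a DLT. Section 4.2 allows non-evaluable subjects in Parts A and B to be replaced.
- **Use of the count:** Appendix 1, Section 1.1 fits the BLRM to DLT data from the 28-day period. Section 3.7 sets the 33% expansion trigger on toxicities that meet DLT criteria.

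**The concern.** Group B takes dermatologic toxicity out of the Grade 3+ default, and group C puts back only part of it. Two kinds of severe drug-related skin event are left without a criterion: those that are not rash, and those that end treatment before there is an infusion to delay.

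Determining DLTs is part of the primary objective (Section 1.4.1), and DLT counts are the on-study data that drive an overdose-control model. A subject stopped for severe skin toxicity could be recorded as having tolerated the dose, or be replaced. Skin toxicity is also foreseeable here: Section 1.6 names rash and pruritus among the most common AEs with nivolumab.

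**Working it through.** The plan states no figure on this point, so there is none to reproduce. The check is to take each kind of drug-related skin event through groups B and C as written. Groups A and D concern liver and blood and do not apply.

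| Event | B default | B named reactions | C | Literal result |
|---|---|---|---|---|
| Grade 3/4 rash, still above Grade 1 after the delay | excluded | no | met | DLT |
| Grade 3/4 rash, Grade 1 or less after the delay | excluded | no | not met | not a DLT, by design |
| Grade 3 pruritus, however long it lasts | excluded | only if so labelled | not rash | not a DLT |
| SJS/TEN diagnosed and treatment ended before an infusion is delayed | excluded | only if so labelled | no delay to judge | not a DLT |
| Grade 5 skin event | excluded | only if labelled a reaction, via the default | names Grades 3 and 4 only | not a DLT |
| Grade 4 event labelled hypersensitivity | applies, since no longer classed as dermatologic | names Grade 3 | – | DLT |

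The fourth row depends on timing. Because suspected SJS/TEN leads first to withholding, a due infusion may be missed and the group C test might then be applied. The gap is the case where treatment is ended between infusions.

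**What happens to the subject in Parts A and B.** Section 3.3.1 keeps a subject who stops treatment in safety follow-up.

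1. If observed to Day 28, the subject is evaluable and, with no criterion met, counts as DLT-free.
2. If not observed to Day 28, the subject is evaluable only if stopped because of a DLT. As the event is not one, the subject may be replaced and the event does not reach the model.

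**Effect on the count.** With one uncounted event, x/n becomes (x − 1)/n. These are illustrative raw proportions, set beside the 16% and 33% boundaries in Appendix 1, Section 3.1:

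- n = 3: 1/3 = 33.3% becomes 0/3 = 0%.
- n = 6: 2/6 = 33.3% becomes 1/6 = 16.7%.
- n = 12, the maximum per dose level: 4/12 = 33.3% becomes 3/12 = 25%.

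The model acts on posterior DLT rates, not raw proportions. Its numerical priors are not in the available text, so the change in recommended dose cannot be computed. The one worked example does not show a harmful change: in Appendix 1, Section 4, one DLT in three at 30 mg in combination still leads to 100 mg (target probability 0.311, against 0.295 at 30 mg and 0.263 at 10 mg).

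**Expansion.** The 33% rule counts only toxicities meeting DLT criteria, so the same events are missing from its numerator.

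**The case against.** The strongest reply is that little turns on this. Dose selection uses all data on dosed subjects and needs agreement between investigators and the Medical Monitor (Section 3.4.1). The AE and SAE tables would show the event. Section 3.7 sends all safety signals to the Medical Surveillance Team, whatever their DLT status, and the 33% trigger only prompts discussion. The December 2016 update reports no DLTs in 34 monotherapy subjects, and Section 3.6.1 treats 800 mg every two weeks as already assessed as safe. All of this stands and limits the consequence. It does not correct the model's input, because these reviews are judgement applied on top of the count.

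A reader might also infer more than the documents support:

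- **That Section 4.3.6(b) shows pruritus was meant to be a DLT.** It lists "Grade 3 pruritus or rash that returns to grade 1 or baseline within 7 days or baseline with medical intervention" as an exception to DLT-based discontinuation. But exception (f) covers Grade 4 lymphopenia, which is not a DLT in 4.3.1 D. The list does not mirror the definition, so intent cannot be read from it.
- **That the hypersensitivity route stops at Grade 3.** The named bullet does, but a Grade 4 or higher event so labelled is no longer dermatologic and falls under the default. That route is limited by labelling, not by grade.
- **That a rash confirmed after Day 28 is lost.** A rash beginning after the Day 15 dose would first delay the Day 29 infusion, so confirmation comes after the window. But Section 3.6 counts by occurrence within four weeks, and Section 3.4.1 and Appendix 1 (Sections 2.2.1 and 4) update the model as DLT data arrive. At most one interim decision precedes confirmation.

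**Conclusion.** The gap is real and should be fixed. On the literal text, drug-related Grade 3+ skin events other than rash, and severe skin events such as SJS/TEN that end treatment before an infusion is delayed, are not DLTs unless labelled as a hypersensitivity or infusion reaction. The direct effect is on data: one DLT fewer per such event in the BLRM, or a replaced subject, and one fewer in the 33% trigger.

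The effect on dose is potential and cannot be quantified. Nothing in the documents shows that such an event occurred or that any dose was chosen wrongly. The conclusion assumes that the definition is applied as written and that the event is coded as a skin event. The grade-by-grade skin algorithm figure in Appendix 4 is not shown, but that appendix gives management guidance and does not define DLTs.

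**What to change.** In Section 4.3.1 C:

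1. Replace Grade 3/4 rash with any drug-related Grade 3 or greater skin event, keeping the existing non-resolution test.
2. Add that the following are DLTs whether or not an infusion was delayed: SJS/TEN, any drug-related Grade 5 skin event, and any drug-related Grade 3+ skin event for which the protocol or Appendix 4 requires permanent discontinuation because of the toxicity itself.

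Clause 2 should rest on event type, grade and mandatory discontinuation. A rule based on any discontinuation would be partly circular, since Section 4.3.6 ends treatment for events that meet DLT criteria. It would also admit stops at the investigator's discretion or the subject's request under Section 3.11.

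Optionally, add one sentence to Section 3.4.1: a subject with an unresolved Grade 3+ skin event that began within 28 days is not entered as DLT-free, or replaced, until the event is classified.

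The cost is wording and, with the optional sentence, an occasional short wait before a dose decision. Because Section 4.3.6 ties permanent discontinuation to DLT criteria, newly counted events would also end treatment unless an exception there applies; the sponsor should confirm that this is wanted. If escalation is complete, the sentence in 3.4.1 changes little, but the definition still governs the expansion trigger and DLT reporting.

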4.3.2 Management Algorithms for Immuno-oncology Agents

Immuno-oncology (I-O) agents are associated with AEs that can differ in severity and duration from AEs caused by other therapeutic classes. Nivolumab and BMS-986156 are considered I-O agents in this protocol. Early recognition and management of AEs associated with I-O agents may mitigate severe toxicity. Management algorithms that have been developed from extensive experience with nivolumab to assist Investigators in assessing and managing the following groups of AEs:

- Gastrointestinal
- Renal
- Pulmonary
- Hepatic
- Endocrinopathies
- Skin
- Neurological
- The clinical nature of AEs noted with BMS-986156 will determine the role of the above algorithms for use in toxicities related to its use in this study.

The algorithms recommended for utilization in this protocol are included in [Appendix 4](#).

4.3.3 Guidelines for Dose Modification

Intra-subject dose escalation or reduction of BMS-986156 or nivolumab is not permitted in this study in order to allow better evaluation of extended safety and efficacy at individual dose levels and schedules.

4.3.4 Dose Delays Due to Toxicity

Subjects who experience a DLT must have study drug held. Subjects who are required to permanently discontinue both study drugs are listed in [Section 4.3.6](#). In addition, all Grade 2 hepatic, pulmonary, renal, gastrointestinal, and neurological AEs should be evaluated and managed per the toxicity management algorithms ([Appendix 4](#)). Subjects not meeting guidelines for permanent discontinuation will be permitted to resume therapy based on the criteria specified below in [Section 4.3.5](#). Subjects eligible to resume study therapy will resume study therapy at the treatment visit following their last received study medication dose.

In Parts A and C, if there is a delay in dosing of BMS-986156 of between 1 -12 days, the procedures at the original scheduled visit should be performed as soon as possible. If the delay is more than

12 days, the visit and dose will be considered missed; the procedures at the next scheduled visit should be performed, and subsequent BMS-986156 doses will follow every 2 weeks.

In Parts B, D and E depending on the dosing schedule (See [Table 5.1-2](#)), if there is a delay in dosing of combination dose (same day dose of BMS-986156 and nivolumab) of between 1 -12 days, If the delay is more than 12 days, the visit and dose will be considered missed; the procedures at the next scheduled visit should be performed, and subsequent combination doses will follow after 2 weeks.

Extensions to the period of dose delays may be granted for individual subjects on a case by case basis after specific consultation and agreement between the Investigator and BMS Medical Monitor in settings where benefit/risk may justify continued study therapy (e.g., subject deriving clinical benefit who requires prolonged steroid taper for management of non-DLT drug-related AEs, or experiences delays for management of a non drug related AE).

The end of cycle tumor assessments (i.e., CT/MRI, positron emission tomography, etc) will continue on an every 8 weeks schedule relative to the subject's 1st dose regardless of any treatment delay incurred.

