3 INVESTIGATIONAL PLAN

3.1 Study Design and Duration

This is a Phase 1/2a, open-label study of BMS-986156 administered as a single agent and in combination with nivolumab in subjects with advanced solid tumors.

The study will be conducted in 5 parts. Parts A and B will consist of dose escalation with BMS-986156 administered as a single agent (Part A) or in combination with nivolumab (Part B) in subjects with advanced solid tumors. Starting dose selection of BMS-986156 for Part B (combination with nivolumab) was determined using all available safety (clinical and laboratory), PK, [REDACTED] and modeling recommendations within Bayesian hierarchical modeling framework by incorporating single agent toxicity profiles of both BMS-986156 (Part A) and nivolumab (data from CA209003 study, a phase 1 nivolumab monotherapy data in advanced solid tumors) and will be one dose level lower than a dose already tested and shown to be tolerated in ongoing monotherapy dose escalation in Part A [REDACTED]. Subsequently, escalation in the 2 parts will proceed in parallel.

A dose -1 cohort of 3 mg has also been included and will only be explored in the event 10 mg dose of BMS-986156 is determined to exceed the MTD in monotherapy or in combination with nivolumab (Table 3.4.1-1).

At no point will the dose of BMS-986156 administered in combination with nivolumab in Part B exceed doses of BMS-986156 that have been demonstrated previously to be safe in the monotherapy dose escalation arm (Part A), nor at any point during Part B escalation will the BMS-986156 dose exceed the highest dose determined to be tolerated in Part A.

Nivolumab will be administered as a dose of 240 mg every 2 weeks for combination dose cohorts (Parts B and D).

Nivolumab will be administered as a dose of 480 mg every 4 weeks for combination dose cohorts Part E

Part C consists of cohort expansion with BMS-986156 monotherapy in 2 disease-restricted populations, NSCLC with progressive or recurrent disease (per RECIST v1.1) during or after anti-PD-1 or anti-PD-L1 therapy following prior platinum doublet-based chemotherapy, and persistent, recurrent, or metastatic cervical cancer, of approximately 40 subjects each.

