The treatment phase consists of up to three 8-week treatment cycles. In Parts A and C, each treatment cycle comprises 4 doses of BMS-986156 administered every 2 weeks on Days 1, 15, 29, and 43 of the treatment cycle. In Parts B and D, each treatment cycle comprises 4 doses of BMS-986156 (administered on Days 1, 15, 29 and 43) in combination with 4 doses of nivolumab administered on Days 1, 15, 29, and 43 of the treatment cycle. In Parts B and D and E when both study drugs are given, nivolumab will be given first followed by BMS-986156 at least 30 minutes after completion of the infusion of nivolumab. In Part E, the cohort of 480 mg/480 mg each treatment cycle comprises 2 doses of BMS-986156 (administered on Days 1 and 29) in combination with 2 doses of nivolumab administered on Days 1 and 29 of the treatment cycle.

Following each treatment cycle, the decision to treat a subject with additional cycles of study therapy, up to a maximum of 13 treatment cycles, will be based on tumor assessment (evaluation performed between Days 49 and 56 of each cycle and completed before the first dose in the next cycle). Tumor progression or response endpoints will be assessed using Response Evaluation Criteria in Solid Tumor (RECIST) v1.1 criteria for solid tumors ([Appendix 3](#)).

Treatment beyond progression may be allowed in select subjects with initial RECIST v1.1-defined progressive disease (PD) after discussion and agreement with the BMS Medical Monitor that the benefit/risk assessment favors continued administration of study therapy (e.g., subjects are continuing to experience clinical benefit as assessed by the Investigator, tolerating treatment, and meeting other criteria specified in [Section 3.11.1.1](#)).

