4.3 Selection and Timing of Dose for Each Subject

Each subject will be assigned to a specific dose level as listed in [Section 4.2](#) in sequential order during dose escalation. Subjects in cohort expansion will be treated at the MTD, the MAD, or at an alternate dose(s), as agreed upon by the Investigators and the Sponsor.

Nivolumab will be administered as flat doses in cohorts B and D at 240 mg and in cohort E, at 480 mg. There will be no dose escalations or reductions of nivolumab allowed once assigned. Subjects may be dosed no less than 12 days from the previous dose. There are no pre-medications recommended for nivolumab on the first cycle. If an acute infusion reaction is noted, the subjects should be managed according to [Section 4.3.7](#).

BMS-986156 will be administered as flat dosing at the doses listed in [Section 1.1.1](#).

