4.3.5 Criteria to Resume Treatment

Subsequent dosing with study therapy may resume once drug-related non-DLT AEs resolve to Grade 1 or baseline.

Subjects experiencing AEs not meeting criteria for permanent discontinuation as outlined in [Section 4.3.6](#) may resume treatment with study medication under the following criteria:

- Subjects may resume treatment with study drug when the drug-related AE(s) resolve to Grade ≤ 1 or baseline value with the following exceptions:
 - Subjects may resume treatment in the presence of Grade 2 fatigue;
 - Subjects who have not experienced a Grade 3 drug-related skin AE may resume treatment in the presence of Grade 2 skin toxicity;
 - Subjects with Grade 2 uveitis or eye pain or blurred vision not meeting DLT criteria ([Section 4.3.1](#)) must resolve to baseline prior to resuming study therapy;
 - Drug-related pulmonary toxicity, diarrhea, or colitis, must have resolved to baseline before treatment is resumed;
 - Drug-related endocrinopathies adequately controlled with only physiologic hormone replacement may resume treatment.

If the criteria to resume treatment are met, the subject should restart treatment at the next scheduled time point per protocol.

The consideration to re-initiate study therapy under these exceptions will be made on a case by case basis after considering the overall benefit/risk profile and in consultation between the Investigator and the study sponsor. Any AE with clinical risk will be assessed on a case by case basis with the Investigator and the BMS Medical Monitor to determine the risks and benefits of continuing on therapy following resolution versus discontinuing therapy permanently.

If treatment with study medication is delayed > 6 weeks, the subject must be permanently discontinued from study therapy, except as specified in Section 4.3.6.

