	Day 1 (± 2 days)	Day 15 (± 2 days)	Day 29 (± 2 days)	Day 43 (± 2 days)	Day 49-56		
Study Drug Administration							Details regarding preparation and administration are provided in site training materials.
Parts A, B, C, and D: BMS-986156 administration	X	X	X	X			Use vials assigned per IVRS.
Part E: BMS-986156 administration	X		X				Use vials assigned per IVRS
Parts B and D ONLY: nivolumab administration	X	X	X	X			Use vials assigned per IVRS. Nivolumab is administered ONLY for those subjects enrolled in Part B (dose escalation, combination therapy) and Part D (cohort expansion, combination therapy).
Part E ONLY: nivolumab administration	X		X				Use vials assigned per IVRS, for subjects enrolled in Part E

Abbreviations: AE, adverse event; ALP, alkaline phosphatase; ALT, alanine aminotransferase; AST, aspartate aminotransferase; BUN, blood urea nitrogen; CRP, C-reactive protein; ECG, electrocardiogram; ECOG, Eastern Cooperative Oncology Group; EOT, end of treatment; GGT, gamma-glutamyl transferase; hCG, human chorionic gonadotropin; IVRS, Interactive Voice Response System; LDH, lactate dehydrogenase; LFT, liver function test; [REDACTED] PE, physical examination; PK, pharmacokinetics; RECIST, Response Evaluation Criteria in Solid Tumor; SAE, serious adverse event; T3, triiodothyronine; T4, thyroxine; TSH, thyroid-stimulating hormone; WOCBP, women of childbearing potential.

- ^a EOT is defined as the visit where decision is made to discontinue the subject from treatment.
- ^b For subject who complete all scheduled cycles of therapy, EOT visit will be the same as the last scheduled and completed on treatment visit (e.g., Cycle 3 Day 43), and the start of week 1 safety follow-up visit.
- ^c For subjects that do not complete all scheduled cycles of therapy, EOT visit will be the most recent on-treatment visit (with all available safety and response data) and does not need to be repeated, and will be considered the start of week 1 safety follow up visit.
- ^d If there is a safety concern (e.g. Grade 3 or 4 AE, SAE, etc.), ad hoc PK and ADA sample collection would be permissible (using an Unscheduled Visit Form).

Table 5.1-3: Follow-up Procedural Outline (CA009002)

Procedure	Safety Follow-up			Notes
	FU 1 30 days ^a (± 7 days)	FU 2 60 days (± 7 days)	FU 3 100 days (± 7 days)	
Safety Assessments				
PE	X	X	X	Symptom directed only.
ECOG performance status	X	X	X	ECOG score (Appendix 2).

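### The Section 4.3.4 restart rule gives Part E a 2-week interval that, after a restart on a dosing day, puts the next 480/480 mg dose on a day with no scheduled dose

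*Combined protocol and SAP*

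**What the plan says.** The third paragraph of Section 4.3.4 begins "In Parts B, D and E depending on the dosing schedule", refers to Table 5.1-2, and covers all three combination parts. If the delay exceeds 12 days, the visit and dose count as missed, the procedures of the next scheduled visit are performed, "and subsequent combination doses will follow after 2 weeks". No 4-week interval appears anywhere in Section 4.3.4. The parallel sentence for the monotherapy Parts A and C, both dosed every 2 weeks, reads "subsequent BMS-986156 doses will follow every 2 weeks".

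The Part E schedule is fixed elsewhere. Section 3.1 states: "Nivolumab will be administered as a dose of 480 mg every 4 weeks for combination dose cohorts Part E". It also gives two doses per 8-week cycle, on Days 1 and 29. In Table 5.1-2 the row "Part E ONLY: nivolumab administration" and the matching BMS-986156 row are marked at Days 1 and 29 only, although Days 15 and 43 are visits for every Part.

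Two other provisions bear on the point. Section 4.3, in the paragraph that sets the 480 mg nivolumab dose for Part E, says: "Subjects may be dosed no less than 12 days from the previous dose". Section 4.3.5 says that once the criteria to resume are met, "the subject should restart treatment at the next scheduled time point per protocol".

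**The concern.** The rule names Part E but states only the interval that suits Parts B and D. It applies to subjects coming back from a hold of more than 12 days, often for toxicity. Part E subjects attend on Days 15 and 43 anyway, so a site that follows the sentence literally after a restart on Day 1 or 29 has the subject present on the day to which the clause points. It could then give a second 480/480 mg dose after 14 days instead of 28. No Part of the study plans nivolumab 480 mg at that spacing with BMS-986156.

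**Working it through.** The plan gives no figure to reproduce. The check compares the rule with the dosing calendar.

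**Inputs**
- Parts B and D: doses on Days 1, 15, 29 and 43 (Section 3.1, Table 5.1-2), so the interval is 15 − 1 = 14 days.
- Part E: doses on Days 1 and 29, so the interval is 29 − 1 = 28 days. Visits fall every 14 days.
- Rule: more than 12 days late means missed; later doses come after 14 days (Section 4.3.4).
- Minimum gap between doses: 12 days (Section 4.3).
- Upper limit on a delay: 6 weeks = 42 days, with exceptions (Sections 4.3.5 and 4.3.6).

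**Step 1: where the rule puts the dose in Part E.** Take a missed Day 29 dose. The following visits are Day 43 (drug-free), Day 57 (dosing day), Day 71 (drug-free) and Day 85 (dosing day). Assume that the next scheduled visit means the first visit on or after recovery, and that no drug is given at a drug-free visit.

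| Hold, days past the due dose | Next visit | Dose 14 days after that visit | Part E dosing day? |
|---|---|---|---|
| 13–14 | Day 43, drug-free | Day 57 | Yes |
| 15–28 | Day 57, restart | Day 71 (Day 15 of its cycle) | No |
| 29–42 | Day 71, drug-free | Day 85 | Yes |

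With the +2-day visit window the bands become 13–16, 17–30 and 31–42 days. In the last band the dose falls 56 days after the due one, so the 6-week limit also comes into play.

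**Step 2: does another rule block it?** The gap is 71 − 57 = 14 days, which exceeds the 12-day minimum. It is not blocked.

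**Step 3: amount of each drug in the 8 weeks from restart (Days 57–112).**
- Planned: Days 57 and 85 → 2 × 480 = 960 mg; 960 / 8 = 120 mg/week.
- Literal rule: Days 57 and 71, then Day 85 if the calendar resumes or Day 99 if 28 days are counted from Day 71 → 3 × 480 = 1,440 mg; 1,440 / 8 = 180 mg/week.
- Ratio: 1,440 / 960 = 1.5.

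**Step 4: the same count with the missed dose included (Days 29–112, 12 weeks).**
- Planned: Days 29, 57 and 85 → 1,440 mg.
- Literal rule: Days 57, 71 and 85 (or 99) → 1,440 mg.
- Ratio: 1.0.

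The defect therefore changes the spacing after the restart, not the total against plan.

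**Step 5: BMS-986156 against tested exposure.** 180 mg/week compares with 800 mg / 2 weeks = 400 mg/week in the highest escalation cohort.

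**The case against.** The strongest reply is that the protocol, read as a whole, already gives the right answer. The clause points to Table 5.1-2, which marks Part E dosing on Days 1 and 29 only, and Section 4.3.5 restarts treatment at a scheduled time point. The next scheduled visit can also mean the visit straight after the missed one. In Part E that visit is always a drug-free Day 15 or 43, and two weeks later is always a dosing day. This is a fair reading, and it shows what was intended. It does not make the sentence right. The pointer introduces the delay condition and supplies no other interval. Section 4.3.5 settles when the subject restarts, not the gap to the dose after that. A site that takes the first visit after recovery is also reading the text fairly.

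The reply is stronger on harm, and much of it stands.
- A reader might infer dosing every 2 weeks throughout: four doses, 1,920 mg in 8 weeks, twice the plan. That needs the word every, which is in the Part A and C sentence; the combination clause says after.
- A reader might take the 1.5 ratio as overall excess exposure. It depends on a window that starts at the restart and leaves out the missed dose.
- A reader might cite Section 3.6.1 as a safety case that the extra dose breaches. That section justifies the 14-day lead-in observation period, not gaps between doses.
- Short gaps are not unique to this clause. If a Part E dose up to 12 days late is given and the calendar kept, as Parts A and C do, the next gap is 28 − 12 = 16 days, or 14 with the visit window. The correction below leaves that possible, so a 14-day gap cannot by itself be the case for change.

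**Conclusion.** The sentence is wrong as written for Part E, within a limited scope. It conflicts with the Part E schedule only when the subject restarts on Day 1 or 29. If the next scheduled visit is the first one on or after recovery, that means holds of 15–28 days (17–30 with the window). The consequence is one off-schedule 480/480 mg dose, giving three doses instead of two in the 8 weeks after restart, with no excess over plan once the missed dose is counted.

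The documents do not support a doubled dose or a demonstrated safety breach. BMS-986156 stays below its tested rate, and Section 1.5.5 reports no maximum tolerated dose for nivolumab monotherapy up to 10 mg/kg. Most drug-related events meeting DLT criteria require permanent discontinuation (Section 4.3.6), and events with clinical risk are reviewed with the Medical Monitor (Section 4.3.5). Part E plans about 2 × 40 = 80 subjects; how many would have such a hold is not given. This is a drafting inconsistency in a dosing instruction. It affects no endpoint definition or planned analysis, but it should be corrected because it governs subjects returning from a hold.

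**What to change.** In the third paragraph of Section 4.3.4, replace the clause giving the 2-week interval with: *subsequent combination doses will follow on the scheduled dosing days for that Part per Table 5.1-2: every 2 weeks in Parts B and D, and every 4 weeks (Days 1 and 29 only) in Part E.*

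Leave the 12-day minimum in Section 4.3 unchanged. Restricting it to the 2-weekly Parts would leave Part E with no stated minimum gap.

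The cost is one sentence and a note to Part E sites. No visits, subjects or analyses are added.
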